	• To determine the maximum, safely tolerated dose of tobramycin solution for inhalation (selected between 78mg, 150mg, 216mg, and 300mg administered every 12 hours) in very preterm infants with BPD who are actively receiving invasive mechanical ventilation and have evidence of a pathogenic GNR bacteria (listed in section 3.4.3) detected by tracheal aspirate culture.
	Secondary
	 To evaluate the association between the dose of inhaled tobramycin, plasma tobramycin pharmacokinetics, and peak tracheal aspirate tobramycin levels.
	• To compare the change (pre vs. post study) in tracheal aspirate pathogenic bacterial colony forming unit (CFU) counts measured by high resolution culture, (1) between participants in the phase 1 trial and untreated infants in the observational cohort, and (2) between trial participants stratified by the administered dose of inhaled tobramycin.
	• To compare the change in measures of administered respiratory support (FiO ₂ , ventilator mean airway pressure, and respiratory severity score) during the 14-day study period, (1) between participants in the observational cohort and phase 1 trial, and (2) between trial participants stratified by the administered dose of inhaled tobramycin.

	• To evaluate changes (pre vs. post treatment) in airway cytokine levels, neutrophil/WBC ratio, and patterns in the airway microbiome.							
	• To compare changes in the following measures of hypoxemia (SpO ₂ <80%): Intermittent hypoxemia (events lasting 10s-3min), prolong hypoxemia (events lasting >1min), and daily proportion of time in hypoxemia during the 14-day study period, (1) between participants in the observational cohort and phase 1 trial, and (2) between trial participants stratified by the administered dose of inhaled tobramycin.							
	• To evaluate longitudinal change in dynamic lung compliance, airway resistance, peak expiratory flow, and CO ₂ elimination during the 14-day study period, (1) between participants in the observational cohort and phase 1 trial, and (2) between trial participants stratified by the administered dose of inhaled tobramycin.							
Study Drug	Tobramycin solution (300mg/5mL) for inhalation USP							
Study Design	Open-label, inter-patient 3+3 dose escalation trial. An untreated observational cohort of eligible infants will also be enrolled and outcomes compared to trial participants.							
Subject Population	Inclusion Criteria							

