2.2 Secondary Objectives

The secondary, exploratory objectives are to:

• Evaluate the association between the dose of inhaled tobramycin, plasma tobramycin pharmacokinetics, and peak tracheal aspirate tobramycin levels.

- Compare the change (pre vs. post study) in tracheal aspirate pathogenic bacterial colony forming unit (CFU) counts measured by high resolution culture, (1) between participants in the phase 1 trial and untreated infants in the observational cohort, and (2) between trial participants stratified by the administered dose of inhaled tobramycin.
- Compare the longitudinal change in measures of administered respiratory support (FiO₂, ventilator mean airway pressure, and respiratory severity score) during the 14-day study period, (1) between participants in the phase 1 trial and observational cohort and (2) between trial participants stratified by the administered dose of inhaled tobramycin.
- Compare changes (pre vs. post treatment) in tracheal aspirate cytokine levels, neutrophil/WBC ratio, and patterns in the airway microbiome, stratified by the administered dose of inhaled tobramycin.
- Change in the following measures of hypoxemia (SpO₂<80%): Intermittent hypoxemia (events lasting 10s-3min), prolonged hypoxemia (events lasting >1min), and daily proportion of time in hypoxemia
- Compare the longitudinal change in dynamic lung compliance, airway resistance, peak expiratory flow, and CO₂ elimination during the 14-day study period, (1) between participants in the observational cohort and phase 1 trial and (2) between trial participants stratified by the administered dose of inhaled tobramycin.

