6.3.3 Exploratory Secondary Safety and Efficacy Analyses

The exploratory secondary safety and efficacy endpoints listed in section 6.2 will be analyzed as described in **Table 7** (next page). In brief, all study data will first be summarized using standard descriptive statistics as appropriate based on data type and distribution. Assessments of change over time for all longitudinal secondary outcome data will first be assessed graphically, with and without stratification by the administered tobramycin dose. Next, paired t-tests or Wilcoxon sign rank tests will be used to compare

pre-trial baseline values to those recorded at later time points. Non-paired tests will be used to compare data baseline and subsequent data points between the infants in the phase 1 trial and observational (non-treated) cohorts.

	Values available for:			
Study outcome	Phase 1 trial cohort	Observational cohort	Statistical approach	
Secondary safety endpoints	Yes	Yes, for some endpoints	 Rates of the secondary tolerability endpoints will be summarized for each dose level. Descriptive, narrative details of these endpoints will also be provided as appropriate. Data on the rates of endotracheal tube obstruction, unplanned tracheal extubation, and audiology testing results will be compared between the trial and observational cohorts. Planned comparisons of audiology testing results are described in the Protection of Human Subjects document. 	
Secondary efficacy endpoints				
Negative TA culture for the target GNR	Yes	No	 Primary exploratory efficacy endpoint. Rates will be summarized for the trial cohort as a whole and stratified by drug dose level. 	
Change in TA GNR pathogen CFU	Yes	No	 Absolute (pre vs post) and relative change ([post trial – pre trial] / pre trial) in the target organism CFU/mL on the log₁₀ scale will be calculated for each phase 1 trial participant. Paired t-tests or Wilcoxon sign rank tests as appropriate will be used to compare pre- vs. post-trial absolute CFU/mL values for the whole cohort and stratified by drug dose level. 	
Tracheal aspirate tobramycin levels	Yes	No	 Values, stratified by drug dose, will be compared to established concentrations necessary to overcome the minimum inhibitory concentration needed to kill 90% of detected bacterial isolates (MIC₉₀).^{90,91} Values will also be used in our PK analyses. 	

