Tracheal aspirate cytokine levels	Yes	No	 Individual cytokine levels measured pre-trial, ≤48 hours after the final dose, and 14 days after the final drug dose will be summarized. Transformation (e.g. logarithmic) or categorization by centiles will be considered based on the data distribution. Correction for total protein levels in the tracheal aspirate will be employed to account for differences in dilution during sample collection. The relative intra-patient change for the individual cytokine levels 	
			 from pre-trial baseline to the 2 post-trial timepoints will be calculated and compared between dose levels. The association between change in cytokine levels and tobramycin dose will be explored using bivariate and multivariate correlation analyses with Bonferroni correction for multiple testing.¹⁰⁰ We will consider exploratory cluster and linear discriminate analyses to identify airway immunological profiles associated with differences in the response to inhaled tobramycin (e.g. change in CFU/mL).^{101,102} 	
Respiratory support measures Hypoxemia (SpO ₂ <80%)	Yes	Yes	 Continuously recorded FiO₂, MAP, and RSS values will be converted to time-weighted daily averages for each study day. Continuously recorded SpO₂ data will be used to calculate daily rates of intermittent and prolonged hypoxemia and daily total hypoxemia exposure. Assessment of longitudinal change using linear mixed effects models will be considered. 	
Pulmonary mechanics	Yes	Yes	 Infants in both study cohorts will undergo pulmonary mechanics measurements pre-trial, after 7d, and after 14d. Intra-patient change, relative to pre-trial baseline, will be calculated for each participant and compared (1) between the two cohorts and (2) stratified by drug dose. Assessment of longitudinal change using linear mixed effects models will be considered. 	

Table 7. Planned statistical techniques and data availability for the phase 1 trial outcomes

CFU, colony forming units; GNR, Gram-negative rod; TA, tracheal aspirate

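### Table 7 treats CFU values in the untreated cohort as unavailable and plans only paired tests in treated infants, so the stated CFU comparison with untreated infants has no analysis of its own.

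*Combined protocol and SAP*

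**What the plan says.** The secondary objective in the Protocol Synopsis is "To compare the change (pre vs. post study) in tracheal aspirate pathogenic bacterial colony forming unit (CFU) counts measured by high resolution culture", and section 2.2 repeats it. In both places the first of two contrasts is "1) between participants in the phase 1 trial and untreated infants in the observational cohort"; the second is by dose among treated infants.

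Section 6.3.3 makes Table 7 the operative analysis plan: "The exploratory secondary safety and efficacy endpoints listed in section 6.2 will be analyzed as described in" that table. In the row for change in GNR pathogen CFU, Table 7 enters Yes for the phase 1 cohort and No for the observational cohort. It states that absolute and relative change on the log10 scale "will be calculated for each phase 1 trial participant", and then gives the test: "Paired t-tests or Wilcoxon sign rank tests as appropriate will be used to compare pre- vs. post-trial absolute CFU/mL values for the whole cohort", with the same stratified by dose. The negative-culture row also carries No for the observational cohort.

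Above the table is one general sentence: "Non-paired tests will be used to compare data baseline and subsequent data points between the infants in the phase 1 trial and observational" cohorts. It names no outcome.

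**The concern.** Followed as written, Table 7 would have the analyst test CFU change only within treated infants and leave the untreated post-study culture out of any CFU analysis. Infants enter because a culture is positive, so some later fall without treatment is plausible, and a one-group pre/post test would credit it to the drug.

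This matters because section 5.3 expects culture change to serve as a surrogate for likely clinical benefit, and section 9.4.3 says the results will inform phase 2 and 3 design. Leaving the matter open also allows the choice between an uncontrolled and a controlled CFU result to be made after the data are seen.

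**Working it through.** **1. Does the plan collect the data that Table 7 marks as unavailable?**

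| Item | Where | Untreated cohort |
|---|---|---|
| Objective to compare CFU change between cohorts | Synopsis; 2.2 | Included |
| Quantitative culture at screening | 5.1.4.1; 5.3 | Scheduled, at most 7 days before the observation period |
| Culture after the study period | 3.1.4; 4.4; 5.1.4.3; 5.3 | Scheduled, within 48 hours after day 14 |
| CFU change in Table 7 | 6.3.3 | No |

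Both values needed for a change score are scheduled, so the No is inconsistent with the plan's own schedule.

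**2. Does other text supply the comparison?** Table 7 can state a cohort comparison when one is meant. In the secondary safety row, tube obstruction, unplanned extubation and audiology results "will be compared between the trial and observational cohorts"; in the pulmonary mechanics row, change is "compared (1) between the two cohorts and (2) stratified by drug dose". The CFU row has nothing similar. The mixed models later in 6.3.3 will only be considered, and only if graphs suggest a linear change.

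**3. Is there a planned CFU figure to reproduce?** No. The only power statement (section 6.4) concerns intermittent hypoxaemia: mean 75, SD 9. A 15% difference is 11.25 events, or 11.25/9 = 1.25 SD, giving 83% power at 12 v 12. An 11% difference is 8.25 events, or 0.92 SD, giving 87% at 24 v 24 (two-sided t-test, alpha 0.05). Both agree with the stated figure of more than 80%, but neither bears on CFU.

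**4. Illustration of what the missing control could cost.** The documents give no mean, SD or spontaneous trend for CFU, so every drift below is an assumption, in units of the SD of within-infant log10 change. Treated cohort sizes: 12 (the lower size in 6.4); 15 = 3+3+3+6 with no toxicity and the expansion at the top dose (4.7.2); 24 (the ceiling, 3.3.2). Untreated cohort sizes: 12 and 28 (6.4).

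*Paired t-test, no drug effect, spontaneous fall of d SD.* The test is noncentral t with n − 1 df and noncentrality d√n, two-sided alpha 0.05. For n = 12 and d = 0.5, the noncentrality is 0.5 × √12 = 1.73.

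| n treated | d = 0.25 | d = 0.5 | d = 0.75 |
|---|---|---|---|
| 12 | 12% | 35% | 66% |
| 15 | 15% | 44% | 77% |
| 24 | 22% | 65% | 94% |

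*Two-sample t-test of change, no drug effect.* It rejects in 5% of trials if both cohorts share the trend. If the trends differ by δ SD, the noncentrality is δ/√(1/n1 + 1/n2). The 95% CI half-width is t(0.975, n1 + n2 − 2) × √(1/n1 + 1/n2); at 12 v 12 that is 2.074 × 0.408 = 0.85 SD.

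| Treated v untreated | δ = 0.25 | δ = 0.5 | CI half-width (SD) |
|---|---|---|---|
| 12 v 12 | 9% | 22% | 0.85 |
| 15 v 12 | 10% | 24% | 0.80 |
| 15 v 28 | 12% | 33% | 0.65 |
| 24 v 28 | 14% | 42% | 0.56 |

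The between-cohort test is not always the safer one. If treated infants fall by 0.25 SD and untreated infants rise by 0.25 SD, then δ = 0.5. At 12 v 12 it rejects in 22% of trials, against 12% for the paired test.

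**The case against.** The strongest reply is that the general sentence on non-paired tests already covers CFU. The respiratory support and hypoxaemia row of Table 7 also names no between-cohort test, yet hypoxaemia is the one cohort comparison the protocol powers (6.4). Silence in a row therefore does not show that no comparison is intended. Likewise, the optional mixed models extend to outcomes collected in both cohorts, and by the sampling schedule CFU is such an outcome. Section 5.3 itself speaks of within-infant CFU change and promises no cohort comparison for it.

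Much of this stands. It would be too strong to say that no between-cohort method exists. But the CFU row is not merely silent: it marks the untreated values as unavailable and confines the calculation to treated infants. The hypoxaemia row is marked Yes for both cohorts, so the general sentence can reach it without contradiction.

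A second reply is that the comparison may not improve inference. Parents choose the cohort. A systemic antibiotic ends trial participation (5.2.4), while in the untreated cohort antibiotics are only recorded (4.5). The treated post-study culture is timed from the last dose, the untreated one from day 14 or extubation (Table 1 footnote b; 4.4). Confounding could run either way, as the second table shows. This limits how the result can be read; it does not justify an availability entry that conflicts with the schedule, or an objective without an analysis.

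**Conclusion.** The concern holds. The objective, the sampling schedule and the CFU row of Table 7 cannot all stand, and this follows from the text alone without any assumed number. The claim is limited: there is no CFU-specific between-cohort analysis, and the general wording elsewhere gives only partial cover.

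The size of the consequence cannot be fixed from the documents. Under the assumed drifts of 0.25 to 0.75 SD, the paired test would give a spurious significant result in 12% to 94% of trials, depending on drift and cohort size. The cohort comparison removes only a trend that both cohorts share, and its precision (±0.56 to ±0.85 SD, unadjusted, equal SDs) suits estimation rather than testing.

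The point should be corrected, but its reach is limited: these endpoints are exploratory, and the primary safety endpoint and dose-escalation decisions do not depend on it.

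**What to change.** - In Table 7, change the observational-cohort entry to Yes in the CFU row, and correct the same availability entry in the negative-culture row.
- In the CFU row, specify the between-cohort difference in log10 CFU change from the screening culture to the culture within 48 hours after the study period, with a 95% CI. State how negative or below-detection cultures enter the log10 calculation; the planned within-treated log10 analysis needs the same rule.
- Label the paired within-treated tests as descriptive.
- Present the comparison as exploratory and non-randomised, and report antibiotic use and culture timing by cohort beside it.

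Adjustment for screening log10 CFU is optional. So is a cohort comparison of culture clearance, which is not a stated objective.

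Deleting the cohort contrast from the Synopsis and section 2.2 would also remove the contradiction, but would leave the scheduled untreated post-study culture without a stated CFU objective.

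The cost is SAP wording and one small analysis. Both untreated cultures are already scheduled, so no sample, visit or infant is added.

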^a "Day 0" procedures to be completed ≤7 days prior to trial Day 1 ^b "Day 15" procedures to be completed ≤48 hours after the final administered dose of inhaled tobramycin (phase 1 trial) or study day 14 (observational cohort)

° Tracheal aspirate sample collected 14 days after the final administered dose of inhaled tobramycin or on the day of planned tracheal extubation, if earlier

^d Serum magnesium and phosphorus levels will be checked with the comprehensive metabolic panel on trial days 7 and 14.

* Up to 6 blood samples (200µL per sample) for pharmacokinetic analyses (PK) will be collected per infant concurrent with clinically ordered blood draws.

page xvi

[figure not shown]

Figure 1. Study enrollment and phases flow diagram.

* Details of both the phase 1 trial and observational (non-treated) cohort will be discussed with eligible families during the consent conversations. Eligible infants may participate in either cohort but can be enrolled in only one cohort.

page xvii

[figure not shown]

Figure 2. 3+3 dose escalation design schematic. MTD: maximum tolerated dose

Up to 4 different dosages of tobramycin solution for inhalation will be investigated using the above 3+3 trial design (78mg, 150mg, 216mg, and 300mg; all administered every 12 hours for up to 14 days). If the 300mg dose level is completed in 3 participants and none show evidence of a toxic response, up to 3 additional infants will be enrolled to receive to receive 300mg. The trial will be stopped if 2 of the additional infants receiving 300mg develop a toxic response and the 216mg dose will be used as the maximum tolerated dose in subsequent trials.

A toxic response is defined as the occurrence of any of the following safety endpoints during the 14-day phase 1 trial (see individual subject and full study stopping rules in section 5.2.4 and 5.2.5 for more details):

- Trough serum tobramycin level (measured 11 hours after the last administered dose) ≥1µg/mL
- Increase in serum creatinine level by ≥0.3mg/dL above the pre-trial level¹⁻³
- Increase in serum creatinine >1.5-fold above the pre-trial level¹⁻³
- Urine output <0.5mL/kg/hr for 12 hours¹⁻³
- Any serious adverse event possibly attributable to the study drug^b

^b The likelihood an adverse event is attributable to a study intervention will be defined as outlined in section 8.3.

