4.3.3 Respiratory mechanics measurements

Respiratory mechanics data will be recorded at 3 timepoints: study entry (day 0 for participants in the phase 1 trial, day 1 for participants in the observational cohort), on study day 7, and ≤48 hours after completion of the 14-day study period. Respiratory mechanics will be measured using a Philips Respironics NM3 respiratory profile monitor placed in-line with the ventilator circuitry. Each recording will last for up to 4 hours. The Respironics sensor will be placed between the Neoflow sensor, if present, or directly to the endotracheal tube if not, and the "y" connector of the ventilator tubing. This device is FDA approved for use in infants (510 (k) K091459). The Respironics NM3 continuously monitors several mechanical and physiological respiratory parameters including minute ventilation, dynamic lung compliance, airway resistance, peak expiratory flow, and carbon dioxide elimination. These data will be downloaded to a dedicated, password protected study computer following each recording session. Respiratory mechanics measurements will be timed to correspond with quiet sleep periods.

The Respironics NM3 monitor sensor adds a negligible amount of dead space to the ventilator circuitry (0.8mL, <3% of inspired tidal volume for eligible study participants) and has been successfully used without adverse effects in infant studies,^{77,78} including those conducted in the CHOP N/IICU (IRB 12-008686). The same procedure for collecting respiratory mechanics data will be used for infants enrolled in the phase 1 trial and those enrolled in the observational cohort.

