5.1.1.2 Phase 1 Trial

The medical record will be reviewed as follows throughout the phase 1 trial:

• Daily review of the medical record and discussion with the medical team, nursing, and respiratory staff to assess for adverse events

- Daily review of weight, vital signs (heart rate, blood pressure, oxygen saturation), and fluid balance (including urine output) recorded by nursing staff in the electronic medical record (EPIC) flow sheet
- Daily respiratory support data (mode of ventilation, settings, FiO₂, and calculated respiratory severity score: mean airway pressure x FiO₂) recorded in EPIC
- Daily review of administered medications (name, dose, route, and interval)
- Daily review of any clinically ordered laboratory tests and radiographic imaging.

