5.1.1.3 Observational (non-treated) cohort

The medical records of infants who are enrolled in the observational cohort will be reviewed daily for 14 days beginning after enrollment. Respiratory support data (mode of ventilation, settings, FiO₂, and calculated respiratory severity score: mean airway pressure x FiO₂) will be abstracted from EPIC.

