5.1.6 Respiratory mechanics measurements

A Philips Respironics NM3 respiratory profile monitor will be used to collect respiratory mechanics data. Measurements will be performed at 3 time points: at study entry (study day 0 for infants enrolled in the phase 1 trial, study day 1 for infants enrolled in the observational cohort), study day 7, and \leq 48 hours after completing the 14-day study period. Each recording period will last 4 hours and coincide with a period of quiet sleep. The NM3 monitor is FDA approved for use in infants (510 (k) K091459). The Respironics NM3 monitor will be used to collect data on the following endpoints: dynamic compliance (mL/cm H₂O), peak expiratory flow (L/min), airway resistance (cm H₂O/L/sec), and carbon dioxide elimination (mL/min). These data will be downloaded to a dedicated, password protected study computer following each recording session. For this analysis, only results obtained from mandatory, ventilator driven non-pressure support breaths will be used.

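### Compliance, peak expiratory flow and CO2 elimination are tested before versus after in absolute units, so growth over the study period can appear as a change in treated infants

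*Combined protocol and SAP*

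**What the plan says.** Section 5.1.6 lists the mechanics endpoints as "dynamic compliance (mL/cm H₂O), peak expiratory flow (L/min), airway resistance (cm H₂O/L/sec), and carbon dioxide elimination (mL/min"). Section 5.3 repeats the same units. Neither section divides by weight, length or lung volume.

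The general text of section 6.3.3 covers all longitudinal secondary outcomes and says that "paired t-tests or Wilcoxon sign rank tests will be used to compare" pre-trial values with later ones. The pulmonary mechanics row of Table 7 is more specific: "Intra-patient change, relative to pre-trial baseline, will be calculated for each participant and compared" between the two cohorts and by dose.

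The baseline recording is at "study entry (day 0 for participants in the phase 1 trial, day 1 for participants in the observational cohort"). Table 1, footnote a, lets day 0 "procedures to be completed ≤7 days prior to trial Day 1". The last recording falls within 48 hours after the study period.

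Weight is collected unevenly. Section 5.1.1.1 takes it once at enrollment. Section 5.1.1.2 has "Daily review of weight, vital signs" and fluid balance for trial infants. Section 5.1.1.3 names only ventilatory support for the observational cohort. Body weight is an analysis covariate only in the population PK model (section 6.3.4).

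**The concern.** These are infants at or beyond 36 weeks' postmenstrual age, followed for two weeks or more. A bigger infant has a bigger lung, produces more CO2 and is given larger breaths. Section 5.3 describes usual practice in the unit as volume-guarantee ventilation at 8-10 mL/kg, and section 5.1.6 restricts the analysis to mandatory ventilator breaths, so delivered volume follows weight by design. Measuring change from the infant's own baseline, even as a percentage, does not remove this: the infant has grown in the meantime.

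A paired test in treated infants cannot separate growth from drug effect. What is at stake is the reading of the mechanics data, which section 5.3 presents as important evidence on respiratory function and section 9.4.3 expects to inform phase 2 and 3 design. A rise in raw compliance or peak flow with a small p-value could be carried forward as a signal of efficacy when it shows only that the infants gained weight.

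**Working it through.** The plan gives no SD, effect size or power for pulmonary mechanics, so there is no stated figure to reproduce. Its only power statement (section 6.4, intermittent hypoxemia, mean 75, SD 9) was run as a check on the method. A two-sample noncentral t gives 83.3% for a 15% difference at 12 per group and 87.5% for an 11% difference at 24 per group. Both agree with the stated figure of more than 80%.

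**Step 1: scaling.** Suppose a measure M is proportional to weight W and the drug does nothing. Then M_later / M_baseline = W_later / W_baseline, so the percentage change in M equals the percentage weight gain. Per kg, (M/W)_later / (M/W)_baseline = 1 and the drift disappears.

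**Step 2: weight range.** Section 4.3.3 puts the sensor dead space of 0.8 mL below 3% of tidal volume, so tidal volume exceeds 0.8/0.03 = 26.7 mL. At 8-10 mL/kg that implies a weight of at least 26.7/10 = 2.7 kg to 26.7/8 = 3.3 kg. Assumed range: 2.7-4.5 kg.

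**Step 3: drift.** Assumed gain is 20-30 g/day. Over 14 days this is 280-420 g.
- Low end: 280/4500 = 6%.
- High end: 420/2700 = 16%.

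The longest trial interval is 7 + 14 + 2 = 23 days, which multiplies these figures by 23/14 = 1.6. The rates below use 14 days only.

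**Step 4: paired test with no drug effect.** The noncentrality is drift × √n / SD, and the test rejects when |T| exceeds the two-sided 5% point on n−1 degrees of freedom. For example, 6% drift, SD 30% and n=12 gives 6 × 3.464/30 = 0.69 and a rejection rate of 10%. The SD of within-infant percentage change (10-30%) is assumed.

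| Drift | n | SD 10% | SD 20% | SD 30% |
|---|---|---|---|---|
| 6% | 12 | 47% | 16% | 10% |
| 10% | 12 | 88% | 35% | 18% |
| 16% | 12 | >99% | 71% | 39% |
| 6% | 24 | 80% | 29% | 16% |
| 10% | 24 | >99% | 65% | 35% |
| 16% | 24 | >99% | 96% | 71% |

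For one dose level with n=6, the range is 7-88%.

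**Step 5: how real n=24 is.** Section 3.3.2 reaches 24 by assuming one toxic response at each of four levels. Those infants stop treatment at the event (sections 4.7 and 5.2.4). With no toxic response the count is 3 + 3 + 3 + 6 = 15 before replacements. So 24 is a ceiling.

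**Step 6: between-cohort contrast.** Equal growth cancels over the common period. What remains is the extra lead of up to 7 days in the trial baseline. At 20 g/day and 4 kg that is 140/4000 = 3.5%; at 30 g/day and 3 kg it is 210/3000 = 7%. At 24 versus 12 infants, the two-sample test then rejects with no drug effect in 16%, 8% and 6% of trials (3.5% lead; SD 10%, 20%, 30%) or 49%, 16% and 10% (7% lead). These figures assume that every trial infant uses the full 7 days, so they are upper values for the given growth and SD.

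**The case against.** The strongest reply is that the plan already has a control. Mechanics are also recorded in untreated infants on nearly the same schedule, and the mechanics row of Table 7 specifies contrasts between cohorts and doses, not a pre/post test. This largely stands for those contrasts: a reader might infer that they are invalid too, but shared growth mostly cancels and nothing in the documents shows that weight gain differs by cohort or dose. It does not rescue the paired tests, which section 6.3.3 applies generally, and the unequal baseline windows leave a residue that favours the treated group where higher values count as better.

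The mixed model in section 6.3.3 has a treatment-week term and room for covariates. It is optional, conditional on a visibly linear trend, does not name weight, and would not correct the paired tests.

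Three stronger readings are tempting and are not supported:
- **That the observational cohort could never be indexed.** Its records are reviewed until discharge (section 4.2), the hospital record is the source document (section 9.2), and enrollment weight is taken. Follow-up weight is unplanned, not shown to be unrecoverable.
- **That growth moves all three measures in a favourable direction.** The documents do not say which direction of CO2 elimination is improvement.
- **That a single inflated error rate can be quoted.** Growth, proportional scaling and SD are all assumed, and ventilator settings also influence flow and CO2 output.

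It is also fair to say that the consequence is limited. These are exploratory endpoints, and Table 7 gives the leading exploratory efficacy role to culture clearance.

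**Conclusion.** The point holds for the paired pre/post tests. Three size-dependent measures are analysed in absolute units with no index, so growth can be read as change in treated infants, most clearly as improvement in compliance and peak flow. The between-cohort contrast is much better protected, but not completely.

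The missing index is certain from the text. The size of its effect is not. Under the assumptions in the working, the false-positive rate is about 10% to nearly 100% at n=12 and 16% to nearly 100% at n=24, against 5%. That width reflects what the documents leave open. Dose escalation, the stopping rules and the primary safety endpoint do not depend on these analyses. The change is worth making before analysis, but it does not threaten the trial's main purpose.

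**What to change.** - In section 5.1.6, section 6.3.3 and the mechanics row of Table 7, state that compliance, peak expiratory flow and CO2 elimination will be analysed per kg of weight on the recording day, with raw units as supporting results.
- In section 5.1.1.3, add charted weight on the three recording days to the observational abstraction.
- In section 6.3.3, label the pre/post mechanics tests as descriptive, to be read beside the between-cohort contrast.

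Indexing would remove drift proportional to weight and return the paired test to about 5% under no effect. It would also remove the growth part of the unequal baseline windows without a change to the visit schedule.

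The cost is SAP wording and three charted weights per observational infant; trial infants' weights are already reviewed daily. The drawback is that weight also moves with fluid status, and diuretics are permitted at entry. Keeping the raw values alongside lets a reader see whether a per-kg change comes from the lung measure or from the denominator.
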